## **9.2.2** Reactogenicity (for Vaccine Studies and Some Therapeutic Trials)

Not applicable

#### **9.2.3** Serious Adverse Events (SAEs)

SAEs (e.g. hospitalization) will be followed for up to 29 days to assess final outcome.

A patient who reports hospitalization and/or an adverse effect of the study drug on a CRF who has not reached out to the team by phone or email will be contacted in a timely fashion and the site doctor made aware. We will review the "positive" CRFs to detect these. We also collect details about the hospitalization.

Patients who do not complete their day 14 CRF will receive reminder emails and, if they do not respond to that, they will be telephoned. Patients must provide an alternate contact at enrollment. If they do not respond to the above means, we will call that contact to find out what has happened. If that person does not know or is not available, we will send registered mail to the address of the patient before concluding loss to follow-up. A sensitivity analysis of the mortality outcome will be performed assuming patients lost to follow-up despite these means have died.

# **9.2.4** Procedures to be Followed in the Event of Abnormal Laboratory Test Values or Abnormal Clinical Findings

Not applicable

# **9.3** Reporting Procedures

#### **9.3.1** Serious Adverse Events

An AE or suspected adverse reaction is considered a serious adverse event (SAE) if it results in any of the following outcomes:

- Death
- life-threatening adverse event (as below),
- Hospitalization
- Persistent or significant incapacity or substantial disruption of the ability to conduct normal life functions, or
- Important medical events that may not result in death, but are life-threatening, or require hospitalizations may be considered serious when, based upon appropriate medical judgment they may jeopardize the patient or subject and may require medical or surgical intervention to prevent one of the outcomes listed in this definition.

Examples of such medical events include allergic bronchospasm requiring intensive treatment in an emergency room or at home, blood dyscrasias or convulsions that do not result in inpatient hospitalization, or the development of drug dependency or drug abuse.

Life-threatening adverse events: An AE is considered "life-threatening" if, in the view of either the site principal investigator or sponsor, its occurrence places the patient or subject at immediate risk of death. It does not include an AE that, had it occurred in a more severe form, might have caused death. For life threatening AEs, subjects would be recommended /expected to be hospitalized.

Based on the known safety track record of ciclesonide, this pragmatic protocol will focus on death, life-threatening AEs, and hospitalizations. Incapacity / permanent disability is a possibility with COVID-19, but this is not associated with ciclesonide. In the event of incapacity, the subject would be expected to be hospitalized.

Ciclesonide can be used in asthmatic pregnant women. However, as per product monograph; "There are no adequate and well controlled studies in pregnant women. However, serum concentrations of ciclesonide are generally very low following inhaled administration; thus, fetal exposure is expected to be negligible and the potential for reproductive toxicity low. As with other inhaled corticosteroids, ciclesonide should only be used during pregnancy when the potential benefit to the mother justifies the potential risk to the mother, fetus or infant. Infants born to mothers who received corticosteroids during pregnancy should be observed carefully for hypoadrenalism." As we don't know the potential benefit of ciclesonide in COVID-19 patients, we will exclude pregnant women for our trial.

Thus, the hospitalization or death secondary endpoint will capture relevant SAEs for those with ongoing hospitalization at the day 14 study visit, participants will be queried in 14-days with the hospital eCRF to assess their final outcome.

## **9.3.2** Regulatory Reporting

As ciclesonide is a Health Canada-approved medicine being used at standard dosing, reporting to regulatory authorities will occur as standard and at a frequency of at least annually.

Serious unexpected suspected adverse reactions (SUSARs) which are not expected with COVID-19 nor listed in the Health Canada package insert will be reported to the IRB.

Those SUSARS which are deemed by an independent medical monitor to be related to the study medicine will be reported to Health Canada and the IRB.

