#### 2.2 Rationale

Current standard of care is supportive care after the diagnosis of COVID-19.

Ciclesonide is a corticosteroid currently used for asthma (in its inhaled form) and nasal rhinitis (in its spray form). It has a very good safety profile. Much higher doses of ciclesonide (up to a single inhalation of 3200 mcg) have been administered to healthy volunteers and were well tolerated (9). As such, inhaled and nasal ciclesonide at the doses of 600mcg BID for 2 weeks will have few adverse events. The usual doses for ciclesonide are:

Standard asthma treatment (ciclesonide, *Alvesco*):

- The recommended dose range for ciclesonide in inhalation is 100 to 800 mcg daily (9).
- The recommended starting dose for most asthmatic patients is 200 mcg daily in Canada (10).
- The maximum dose of 800 mcg daily should be administered as 400 mcg twice daily (9).

Standard allergic rhinitis treatment (ciclesonide, *Omnaris*) (11):

- The recommended dose of OMNARIS is 200 mcg per day administered as 2 sprays (50 mcg/spray) in each nostril once daily.
- The maximum total daily dosage should not exceed 2 sprays in each nostril (200 mcg/day)

As the specific dose of ciclesonide to decrease SARS-CoV-2 is unknown, we planned to give a higher dose than the maximum approved dose for asthma of inhaled ciclesonide (1200 mcg daily administered as 600 mcg twice daily) plus the usual dose of intranasal ciclesonide (200 mcg/day) for 14 days. Given viral replication begins in the nasal cavity and then progress to the lungs, we have chosen to administer ciclesonide both intranasally and inhaled. This dose has been chosen in order to maximize deposition of the study drug in the lower airways. Although the usual dose of ciclesonide for asthma is 400 mcg twice daily (for a total of 800 mcg/day), single doses (up to 3200 mcg) have been administered to healthy subjects without significant side effects (9).

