#### **Common Clinical Trial Adverse Drug Reactions (≥1% - <10%)**

Respiratory: Paradoxical bronchospasm (1.6%), Dysphonia (1.0%).

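### Section 9.3.2 calls the dosing standard and judges expectedness by the package insert, though the inhaled dose is 1.5 times the stated maximum; separately, the Summary's SAE measure is not carried into Section 11

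*Combined protocol and SAP*

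**What the plan says.** On dose, Section 2.2 gives the labelled ceiling for the inhaled product: "The maximum dose of 800 mcg daily should be administered as 400 mcg twice daily". It then says openly that "we planned to give a higher dose than the maximum approved dose for asthma of inhaled ciclesonide", namely 600 mcg twice daily for 14 days. The nasal dose, 200 mcg a day, is the labelled one.

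On reporting, Section 9.3.2 opens with "As ciclesonide is a Health Canada-approved medicine being used at standard dosing" and concludes that regulators will be informed in the standard way, at least once a year. It sends to the IRB those serious unexpected suspected reactions "which are not expected with COVID-19 nor listed in the Health Canada package insert will be reported to the IRB". Of these, the ones that an independent medical monitor judges related to study medicine also go to Health Canada.

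On safety outcomes, the Summary names a measure: the cumulative incidence of SAEs and of Grade 3–4 adverse events, with a named grading table. Section 9.3.1 defines SAEs broadly, then narrows: "this pragmatic protocol will focus on death, life-threatening AEs, and hospitalizations". It adds that "the hospitalization or death secondary endpoint will capture relevant SAEs". Section 3.2.2 lists two outcomes of this kind: admission related to SARS-CoV-2 at Day 14, and mortality at Days 14 and 29. Section 11.4 specifies comparisons for the primary and the listed secondary outcomes and contains no safety analysis.

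**The concern.** The main issue is that a reporting rule stands on a factual premise that the same protocol contradicts. Whether a serious reaction is expected decides whether it enters the SUSAR route at all. Under Section 9.3.2 a reaction that the insert lists does not enter it. The label's dose ceiling is below the trial's inhaled dose, so a listing there is weak ground for calling a serious reaction expected here. What is at stake is the reporting of serious reactions at an above-label dose.

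The second issue is one of follow-through. Section 9.3.1 treats a secondary endpoint as the vehicle for SAEs, but the listed outcomes are narrower than the SAE definition. The Summary's broader measure has no population, method or by-arm presentation in Section 11. A reader of the final report could not tell from the plan how SAEs outside the listed outcomes will be shown.

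**Working it through.** **Dose.** Inputs, all from Section 2.2: inhaled 600 mcg twice daily, inhaled maximum 800 mcg a day, nasal dose 200 mcg a day, nasal maximum 200 mcg a day.

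- Inhaled daily dose: 600 × 2 = 1200 mcg, which reproduces the protocol's own figure.
- Inhaled ratio: 1200 / 800 = 1.5, or 50% above the stated maximum.
- Nasal ratio: 200 / 200 = 1.0.

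The dosing premise in Section 9.3.2 is therefore right for the nasal product and wrong for the inhaled one.

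**Expectedness.** Section 9.3.2 has two grounds for leaving a reaction out of the SUSAR route: it is expected with COVID-19, or it is in the insert. Neither ground mentions dose or severity. The further step to Health Canada applies only to events already classed as SUSARs, so a listed reaction reaches neither step of that route.

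**SAE coverage.** The kinds of SAE in Section 9.3.1 compare with the outcomes in Section 3.2.2 as follows.

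- Death: counted, at Days 14 and 29.
- Admission related to COVID-19 by Day 14: counted.
- Admission related to COVID-19 that first occurs after Day 14: not in a listed outcome, although Sections 4.2 and 9.2.3 follow SAEs to Day 29. Section 7.4 gives a half-life of about 6 hours, so such events would be largely off drug.
- Non-fatal admission for another cause: an SAE by definition, but in no listed outcome.
- Important medical event managed without admission: can be an SAE by definition, but in no listed outcome.
- Life-threatening or incapacitating event: Section 9.3.1 expects admission. A non-fatal one then counts only if the admission is related to COVID-19 and falls by Day 14.

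Grade 3–4 adverse events appear in the Summary but in neither Section 3.2.2 nor Section 11.

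**Data.** The Section 7 schedule queries hospitalisation and side effects at every questionnaire from Day 1 to Day 29. Section 7.4 asks about hospitalisation or SAEs at Day 14. Section 7.6 opens a new case report form for contacts that may reflect an SAE. Section 9.2.3 has staff contact participants who report an admission or a drug side effect. The gap is therefore in the specified analysis more than in data capture.

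**The case against.** The other side has good points. Section 2.2 discloses the dose plainly and cites single inhalations of up to 3200 mcg tolerated by healthy volunteers. The Summary already commits to a safety measure, and in a placebo-controlled trial results by arm are the natural reading. Not capturing minor adverse events is a stated pragmatic choice (Section 9.2.1). The Section 9.3.1 sentence about the endpoint runs on into follow-up of participants still in hospital at Day 14, so a full stop may be missing and it may not be meant as a general rule. Section 9.5 describes the DSMB meetings in the past tense, so a changed SUSAR rule may have little left to act on.

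Most of this stands, and it limits the second issue to an analysis that was promised but not specified. It does not rescue the dosing premise: tolerability of single doses bears on risk, but does not make 14 days at 1200 mcg a day standard. However the Section 9.3.1 sentence is punctuated, no listed endpoint fits its description.

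A reader might infer more than the documents support:

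- **That bronchospasm shows both gaps at once.** The SAE example in Section 9.3.1 is "allergic bronchospasm requiring intensive treatment in an emergency room or at home", whereas the reaction listed in Section 2.3.1 is the paradoxical type, at 1.6% with no severity given. These are different events. The allergic type is not on the reproduced list, so it could qualify as unexpected.
- **That listed serious reactions will be reported only once a year.** The text sets a minimum frequency and says reporting follows the standard; it does not exclude faster reporting.
- **That no safety comparison is intended.** The Summary points the other way.
- **That an event was misreported or that harm is likely.** Nothing in the documents shows either.

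**Conclusion.** The point holds, and it should be corrected. Section 9.3.2 is wrong as written: its premise conflicts with Section 2.2 by a factor of 1.5 on the inhaled dose, and its expectedness rule takes no account of that. The ratio is exact arithmetic on the protocol's figures. The criticism of the expectedness rule assumes that the insert's listings reflect use up to the labelled maximum; the insert itself is not in the documents.

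The SAE issue is real but smaller. Non-fatal admissions unrelated to COVID-19 and SAEs without admission are in no listed outcome, and Section 11 does not take up the Summary's measure. How often such events would occur cannot be sized from the documents. The primary efficacy inference is unaffected.

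**What to change.** In Section 9.3.2, replace the dosing clause with a statement that the inhaled dose is above the labelled maximum and the nasal dose is as labelled. Add one sentence: a serious suspected reaction is not classed as expected solely because the insert lists it at lower doses. The downside is possibly a few more SUSAR reports.

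In Section 11, carry the Summary's measure forward as one descriptive table by arm, in participants who took at least one dose. It should cover all SAEs, including all-cause hospitalisation through Day 29, with events that start after Day 14 shown separately. Include Grade 3–4 adverse events where the collected responses allow grading. The side-effect form is not shown, so whether they do is unknown; if they do not, limit the Summary measure to SAEs and report the side-effect responses by arm as collected. Amend the Section 9.3.1 sentence to point to this table.

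The table should stay descriptive. Even with 159 treated participants and no SAE in that arm, the one-sided 95% upper bound on the rate is 1 − 0.05^(1/159) = 1.9%. That figure describes the table's precision and is not evidence of harm. The cost is a clause and a sentence in Section 9.3.2, one table, and some grading work on data already being collected.

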## **9.3.3** Reporting of Pregnancy

We are excluding women who are pregnant, and we will ask child-bearing age women participants to use a contraceptive measure during the trial. Methods of contraception include hormonal contraceptives (e.g. combined oral contraceptives, patch, vaginal ring, injectables, and implants); intrauterine device (IUD) or intrauterine system (IUS), and/or barrier methods of contraception while on the study drug.

## 9.4 Type and Duration of Follow-up of Subjects after Adverse Events

Participants who are hospitalized for COVID-19 or SAEs will have up to 29 day follow up conducted to assess their final outcome. As this is a distance study, management or complications of COVID-19 will need to be as per the participant's local healthcare provider.

#### 9.5 Safety Oversight (DSMB)

A DSMB was formed and met at 50% enrolment and when trial enrolment dropped off. There were no early stopping criteria defined. Members included: [name] MD, [name] MD and [name] MD

# 10 CLINICAL SITE MONITORING

Clinical site monitoring is conducted to ensure that the rights and well-being of trial subjects are protected and that the reported trial data are accurate, complete, and verifiable. Clinical monitoring also ensures that conduct of the trial is in compliance with the currently approved protocol/ amendment(s), ICH, GCP, and with applicable regulatory requirement(s) and Sponsor requirements. Clinical monitoring will also verify that any critical study procedures are completed following specific instructions. Monitoring in Canada will be the responsibility each Site PI under the overall responsibility of [name], RI-MUHC.

The automated logic of the REDCap database system will enable complete records. All data are by self-report.

# 11 STATISTICAL CONSIDERATIONS

## 11.1 Study Hypotheses

We hypothesize that ciclesonide is superior to placebo for reducing dyspnea due to COVID-19 disease among who are symptomatic.

## **11.2** Sample Size Considerations

Our primary outcome is the proportion of patients with resolved respiratory symptoms (fever, cough, shortness of breath, chest congestion or chest tightness) at day 7.

This study is powered based on determining if there is a 15% increase in our primary outcome, the proportion of participants with no symptoms of shortness of breath (including chest congestion and chest tightness), cough or fever at Day 7. Based on the assumption that, by Day 7, 65% of untreated subjects, and 80% of treated subjects, will have resolved their symptoms, we will need 159 subjects per group to detect this difference with 80% power (5% alpha). This analysis has been adjusted to include a 15% dropout rate. The total number of study participants required is 318. These assumptions were made based on another outpatient RCT evaluating symptoms in COVID-19(15).

% Resolved by Day 7- Placebo arm	% Resolved by Day 7- Treatment arm	Proportion difference	Nominal Power, p=0.05	Total participants	Total participants including 15% drop out
75%	85%	10%	0.8	250	
75%	90%	15%	0.8	200	
75%	95%	20%	0.8	98	
70%	80%	10%	0.8	586	
70%	85%	15%	0.8	240	
70%	90%	20%	0.8	124	
70%	95%	25%	0.8	70	
65%	75%	10%	0.8	656	
65%	80%	15%	0.8	276	318 (159 per arm)
65%	80%	15%	0.9	368	
65%	85%	20%	0.8	144	
65%	90%	25%	0.8	86	
60%	70%	10%	0.8	712	
60%	75%	15%	0.8	304	
60%	75%	15%	0.9	406	
60%	80%	20%	0.8	162	
60%	85%	25%	0.8	98	
60%	90%	30%	0.8	62	

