Exclusion Criteria	
 
Already on inhaled corticosteroid medication
 
Currently using systemic steroids (oral or intravenous or intramuscular such as Prednisone) or use of steroids 7 days prior to enrolment
 
Severely ill patients at enrollment (i.e., admitted to ICU at admission)
 
Unable to self-administer the inhaler
 
Known or suspected pregnancy and breastfeeding
 
Known allergy to study medication or its components (non-medicinal ingredients; including lactose allergy (type I))
 
Patients with untreated fungal, bacterial or tubercular infections of the respiratory tract
 
Current hospitalization
 
Current use of oxygen at home or in hospital
 
Vaccinated for COVID-19
 

Stratification	Randomization will be stratified by sex
Statistical Assumptions	With 159 subjects per arm we will be able to detect an absolute increase of 15% in the number of patients with resolved symptoms at day 7.
Safety	Safety of the intervention will be assessed by the cumulative incidence of Grade 3 and 4 AE and SAEs using the Division of AIDS Table for Grading Severity of Adult and Pediatric Adverse Events version 2.1

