#### **5.3.3** Subject withdrawal criteria

Participants may withdraw at any time point at their discretion. Subject withdrawal is defined as decision to terminate trial treatment. Subject will be replaced until the targeted 318 patients required for our power calculation. Study recruitment will be on a rolling basis. Our accrual ceiling is 2 times the required number of participants for the study. Based an alpha of 0.05 and a 15% subject dropout rate, we require 159 participants per arm. Our current power calculations account for a 25% subject dropout rate. As such, should individuals drop out (ie. be lost to follow up), it is unlikely to affect the study error.

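### The 15% dropout allowance in section 11.2 was multiplied on rather than divided out, so 318 participants cover about 13% loss, not 15%

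*Combined protocol and SAP*

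**What the plan says.** Section 11.2 assumes that "by Day 7, 65% of untreated subjects, and 80% of treated subjects, will have resolved their symptoms". From this it concludes that "we will need 159 subjects per group to detect this difference with 80% power (5% alpha"), and adds: "This analysis has been adjusted to include a 15% dropout rate". In the table, the row for 65% versus 80% at power 0.8 gives a total of 276 before dropout. In the column that includes 15% dropout it gives "318 (159 per arm"). The text repeats the total: "The total number of study participants required is 318". The inflation formula is not given.

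Section 5.3.3 ties the same size to the same allowance: "Based an alpha of 0.05 and a 15% subject dropout rate, we require 159 participants per arm". Its next sentence says the power calculations account for 25% dropout. It also provides for replacing subjects up to the target of 318.

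The Summary carries the per-arm figure, saying "With 159 subjects per arm we will be able to detect an absolute increase of 15" points, but gives neither a power nor a dropout rate.

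**The concern.** Two cells of one table row do not fit together under the stated allowance. If 15% of 318 enrolled participants are lost, fewer than the 276 required by that row remain. The pattern is that of adding 15% of the evaluable number instead of solving for the enrolment that leaves the evaluable number after 15% loss.

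At stake is the link between three stated design figures: sample size, dropout allowance and power. An ethics board or journal re-deriving the number from 15% loss will not arrive at 318. The point is separate from the 15% versus 25% conflict in section 5.3.3, because settling that conflict at 15% would leave this error in place.

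**Working it through.** **Inputs.** From section 11.2: p1 = 0.65, p2 = 0.80, alpha 0.05, power 0.80, 276 before dropout, 318 after, dropout 15%. Equal allocation follows from 159 per arm. Sidedness is not stated. I take two-sided, which reproduces the plan's figure; one-sided gives 109 per arm and does not.

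**Step 1: reproduce 276.** Pooled-variance normal approximation without continuity correction, with mean proportion 0.725:

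n per arm = [1.960 x sqrt(2 x 0.725 x 0.275) + 0.842 x sqrt(0.65 x 0.35 + 0.80 x 0.20)]^2 / 0.15^2 = [1.960 x 0.6315 + 0.842 x 0.6225]^2 / 0.0225 = 137.9, rounded up to 138.

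2 x 138 = 276, an exact match.

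**Step 2: reproduce 318.**

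- Multiplying on: 276 x 1.15 = 317.4 (138 x 1.15 = 158.7 per arm), rounded up to 159 per arm, or 318. This is the plan's figure.
- Dividing out: 276 / 0.85 = 324.7 (138 / 0.85 = 162.4 per arm), rounded up to 163 per arm, or 326.

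The difference is 326 - 318 = 8 participants, 4 per arm, or 8/318 = 2.5%.

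**Step 3: the loss that 318 covers.** 1 - 276/318 = 0.132, or 13.2%.

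**Step 4: what remains at 15% loss.** 318 x 0.85 = 270.3, or about 135 per arm, against the required 138.

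**Step 5: power for 65% versus 80%, two-sided 0.05.**

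| Method | 138 per arm | 135 per arm |
|---|---|---|
| Pooled normal approximation (reproduces 276) | 80.0% | 79.1% |
| Exact enumeration, chi-square test | 80.3% | 79.6% |
| Unpooled normal approximation | 80.8% | 79.9% |

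With 326 enrolled and 15% lost, 326 x 0.85 = 277.1 remain (138.55 per arm) and pooled power is 80.2%.

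**For scale: the 25% figure in section 5.3.3.** 25% loss would need 276/0.75 = 368. With 318 enrolled, 318 x 0.75 = 238.5 remain (about 119 per arm), and power is about 74% pooled or 75% unpooled.

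**The case against.** The strongest objection concerns the consequence. The plan states power only as 80% or 0.8. At 135 per arm the exact and unpooled figures both round to 80%, and only the pooled approximation rounds to 79%. The planned primary analysis in section 11.4 is an absolute risk difference from binomial regression, for which the unpooled variance is the closer match. This stands. A reader might infer that the trial is underpowered at its own dropout rate, and the documents do not support that. Restating the power as about 79% would also be a poor remedy, since most methods give a figure that rounds to 80%. The unpooled formula does not, however, justify 318 as derived: it needs only about 135 per arm before dropout and so is not the source of 276.

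Second, section 5.3.3 provides for replacement, with an accrual ceiling of twice the required number, and this could absorb 8 participants. That is possible but not established. The replacement target is 318 rather than 276 evaluable, withdrawal is defined there as stopping treatment, and the text does not clearly say that losses are replaced beyond 318 randomised.

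Third, the documents do not define dropout as a missing day 7 outcome. Participants who stop the drug are still followed (section 5.3.4), and the modified intention-to-treat set asks for one dose and one follow-up assessment (section 11.4). This stands as a caveat: 135 evaluable per arm is what follows if the 15% means participants lost from the primary analysis, which is the reading under which a sample size is normally inflated.

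A reader might also infer that the Summary is wrong. It is not: it states no power and no dropout rate, so nothing in it conflicts with this point.

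**Conclusion.** The point holds as a minor arithmetic correction. The 318 in section 11.2 comes from multiplying by 1.15; the enrolment that preserves 276 after 15% loss is 326 with equal arms. The stated size covers about 13% loss. At 15% loss the shortfall in power is under 1 point, at about 79% to 80% depending on the formula, and it does not threaten the trial.

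This rests on a two-sided test, on dropout meaning loss from the primary analysis as a share of those enrolled, and on no replacement beyond 318. The 25% statement in section 5.3.3 is a separate and larger inconsistency. Correcting either one leaves the other in place.

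**What to change.** In sections 11.2 and 5.3.3, do one of the following:

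- keep 318 (159 per arm) and state that it allows for about 13% loss; or
- keep the 15% allowance and give 326 (163 per arm) as the figure that matches it.

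In either case, add that the allowance is calculated as the evaluable number divided by one minus the dropout rate. Make the edit together with reconciling the 15% and 25% statements in section 5.3.3, so that one dropout rate and one inflated size appear throughout. If 318 is kept, the Summary's 159 per arm needs no change.

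The cost is wording only. No extra enrolment is required, since the effect on power is too small to justify it; under the first option the stated dropout allowance becomes slightly less favourable.
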